2.3.2.3. NT-proBNP Slope over 12 Months of Treatment

The cardiac biomarker NT-proBNP provides important prognostic information in patients with AL amyloidosis and it has been demonstrated that decreasing NT-proBNP levels predict lower mortality rates (Palladini 2010). All visits after the first infusion of study drug will be included up to and through the EEOS visit to evaluate 12 months of treatment.

2.3.3. Additional Secondary Efficacy Endpoints

2.3.3.1. Renal Evaluable Subjects: Renal Best Response from Baseline through 12 Months of Treatment

The Renal Evaluable Population will include subjects who had renal involvement (i.e., proteinuria >0.5 g/24 hours [measured by 24-hour urine total protein excretion]) at baseline and at least one post-baseline assessment of proteinuria. All visits after the first infusion of study drug up and through the EEOS visit will be included to evaluate 12 months of treatment.

For these subjects, renal response categories (modified from Palladini 2014; Appendix 2) are defined as:

Response	Stable	Progression
≥ 30% decrease from baseline or < 0.5g/24 hours post-baseline result of proteinuria (measured by 24-hour urine total protein excretion) in the absence of renal progression	Assessment was neither Response nor Progression	≥ 25% decrease in eGFR from baseline Note: if assessment qualifies as both Response and Progression, then assessments will be counted as progression

Best response is defined as the most favorable category (response, stable, or progression) across all visits. Subjects will be classified as responders or non-responders. Non-response is defined as either stable or progression.

2.3.3.2. Peripheral Neuropathy Evaluable Subjects: Change from Baseline to 12 Months of Treatment in Neuropathy Impairment Score–Lower Limbs (NIS-LL) Total Score

The Peripheral Neuropathy Evaluable Population will include subjects who had peripheral nerve involvement at baseline (only if the subject had ascending sensorimotor neuropathy due to AL amyloidosis etiologies at screening answered as yes) and had a baseline NIS-LL score of 2 or greater and at least one post-baseline peripheral neuropathy assessment. All visits will be included in the model (Section 8.9.2), with the primary comparison at the EEOS visit to evaluate 12 months of treatment.

NIS-LL is a scoring system graduated from 0 points to a maximum of 88 points (the absence of all motor, sensory, and reflex activity in the lower extremities) (Dyck 1995; Appendix 3). The

scale is additive of all deficits (64 potential points for muscle strength, 8 points for reflexes, and 16 points for sensory function) in the lower extremities. The component scores will be calculated by summing the values of the following assessments:

- Sensory Function (in the great toe) = Sum of (touch pressure, pinprick, vibration, joint position)
- Reflexes = Sum of (knee, ankle)
- Muscle Strength = Sum of (hip flexion, hip extension, knee flexion, knee extension, ankle dorsiflexion, ankle plantar flexion, toe extension, toe flexion)
- Total score = Sum of (sensory function, reflexes, muscle strength)

2.3.3.3. Hepatic Evaluable Subjects: Hepatic Best Response from Baseline through 12 Months of Treatment

The Hepatic Evaluable Population will include subjects who had hepatic involvement defined as $>1.5 \times$ ULN alkaline phosphatase (ALP) at baseline and at least one post-baseline assessment of ALP. All visits after the first infusion up to and through the EEOS visit will be included to evaluate 12 months of treatment.

For these subjects, hepatic response categories are modified from Table 2 in [Comenzo, 2012 \(Appendix 2\)](#), where response categories are defined as:

Response	Stable	Progression
$\geq 50\%$ decrease in alkaline phosphatase from baseline	Assessment was neither Response nor Progression	$\geq 50\%$ increase in alkaline phosphatase from baseline

Best response is defined as the most favorable category (response, stable, or progression) across all visits. Subjects will be classified as responders or non-responders. Non-response is defined as either stable or progression.

2.3.4. Exploratory Efficacy Endpoints

The following exploratory efficacy endpoints will evaluate NEOD001 compared to placebo:

2.3.4.1. Cardiac Endpoints

2.3.4.1.1. Cardiac Biomarkers (NT-proBNP and Troponin T)

- Cardiac response ([Appendix 2](#)), as assessed by NT-proBNP response criteria, at each visit
- Cardiac best response (Section 2.3.1), as assessed by NT-proBNP response criteria, through 3, 6, and 9 months of treatment
- Change and percent change from baseline to each visit in NT-proBNP and troponin T

2.3.4.1.2. Select Echocardiogram Cardiac Parameters

- Change and percent change from baseline to each visit in selected cardiac parameters, as determined by a 4-chamber view from a 2-dimensional echocardiogram with Doppler, as follows:
 - LVEF = Left ventricular ejection fraction
 - IVSd = Intraventricular septal at end diastole
 - LPWd = Left posterior wall at end diastole

2.3.4.2. Functional Endpoint

2.3.4.2.1. 6MWT Distance

- Change and percent change from baseline to each visit in the 6MWT distance (meters) (except the key secondary endpoint)
- Categorical analysis of change from baseline to each visit in the 6MWT distance (meters)

2.3.4.3. Quality of Life Endpoints

2.3.4.3.1. SF-36v2

- Change and percent change from baseline to each visit in SF-36v2 PCS score (except the key secondary endpoint), MCS score, and the eight subscales

2.3.4.3.2. KCCQ

The KCCQ is a self-administered, 15-item questionnaire to assess physical limitation, symptom stability, symptom frequency, symptom burden, total symptom score, self-efficacy, quality of life, social limitation, overall summary score, and clinical summary score ([Appendix 8](#)). Scores are transformed to a range of 0-100, in which higher scores reflect better health status. The change and percent change from baseline to each visit in the KCCQ subscores and overall summary score will be evaluated.

2.3.4.4. Renal Endpoints

The following endpoints will be evaluated in the Renal Evaluable Population, unless otherwise specified.

2.3.4.4.1. Renal Response

- Renal response ([Appendix 2](#)) at each visit
- Renal best response through 3, 6, and 9 months of treatment

2.3.4.4.2. Renal Biomarkers

- Change and percent change from baseline to each visit in renal biomarkers (urine albumin/creatinine ratio, urinary neutrophil gelatinase-associated lipocalin [NGAL] and urinary retinol-binding protein [RBP]) in the Renal Evaluable Population and ITT Population

2.3.4.4.3. Creatinine, Proteinuria, and Estimated Glomerular Filtration Rate (eGFR)

- Change and percent change from baseline to each visit in creatinine, proteinuria, and eGFR in the Renal Evaluable Population and ITT Population
- Shifts from baseline in Chronic Kidney Stage in the Renal Evaluable Population and ITT Population

2.3.4.5. Peripheral Neuropathy Endpoints

The following endpoints will be evaluated in the Peripheral Neuropathy Evaluable Population.

2.3.4.5.1. NIS-LL Total Score

- Change and percent change from baseline to each visit in the NIS-LL total score (except the additional secondary endpoint)
- Peripheral neuropathy response ([Appendix 2](#)) at each visit

2.3.4.5.2. NIS-LL Component Scores

- Change and percent change from baseline in the three NIS-LL component scores (sensory function, reflexes, muscle strength) to each visit

2.3.4.5.3. Visual Analog Scale – Pain Intensity (VASPI)

- The VASPI assesses a subject's level of pain related to peripheral neuropathy on a scale from 0 – 100 mm, where 0 is no pain and 100 is the worst imaginable pain ([Appendix 4](#)). For peripheral neuropathy evaluable subjects with painful neuropathy, defined as a baseline VASPI score > 0, change and percent change from baseline in the VASPI score to each visit

2.3.4.6. Hepatic Endpoints

The following endpoints will be evaluated in the Hepatic Evaluable Population.

- Hepatic response ([Appendix 2](#)) at each visit
- Hepatic best response through 3, 6, and 9 months of treatment
- Change and percent change from baseline to each visit in ALP

2.3.4.7. Additional Time-to-Event Endpoints

- Time to All-Cause Mortality (Overall Survival): Any after the first infusion of study drug (i.e. study day 1) through the study's last subject last visit (LSLV). Time (months) to event will be calculated as: (date of death - the date of first study drug infusion + 1) / 30.4375. Subjects will be censored at their last assessment known to be alive prior to LSLV.
- Progression free survival: Time (days) to event will be calculated as the earliest of event dates (cardiac disease progression or death) minus the date of first infusion of study drug plus 1.

- Duration of Cardiac Response: Time (days) to event will be calculated as the earliest date of disease progression subsequent to the first response minus the date of first response plus 1. Subjects never achieving response are excluded.
- Time to derived organ progression for each organ (cardiac, renal) separately
- Time to cardiac or renal progression
- Time to first organ response for each organ (cardiac, renal) separately
- Time to cardiac or renal response

2.3.4.8. Other Efficacy Endpoints

2.3.4.8.1. Cardiac Hospitalizations

- Frequency of cardiac hospitalizations over the course of the study

2.3.4.8.2. ECOG Performance Status, NYHA Class, Renal Stage

- ECOG Performance Status, NYHA Class, and Renal Stage at each visit including any changes from baseline

2.3.4.8.3. Selected Hematological and Urine Analyte Endpoints

- Change and percent change from baseline to each visit in serum free light chains (FLCs), serum and 24-hour urine PEP, and serum and urine IFE

2.3.4.8.4. Disease-Related Symptoms

Disease-related symptoms include macroglossia, submandibular nodes/fullness, adenopathy, ecchymoses, edema, ascites, and liver/spleen size. [Table 2](#) defines each symptom's scoring.

Table 2: Disease-Related Symptoms Scoring

Symptom	Score	Definition
Macroglossia	0	Absent
	1	Patient reports that tongue is enlarged and it appears mild to the observer. Patient is able to close mouth and swallow without difficulty.
	2	Patient reports difficulty in swallowing but is able to close mouth fully.
	3	Patient is unable to close mouth fully but able to swallow.
	4	Patient has significant difficulties in swallowing fluid or food.
Submandibular nodes/fullness	0	Absent
	1	Fullness but no discrete adenopathy identified by observer
	2	Discrete adenopathy, largest lymph node (LN) \leq 2 cm

Symptom	Score	Definition
	3	Discrete adenopathy, largest LN >2 cm but ≤ 4 cm
	4	Discrete adenopathy, largest LN >4 cm
Adenopathy	0	Absent
	1	Discrete adenopathy in ≤ 2 LN stations identified by observer
	2	Discrete adenopathy in > 2 LN stations, largest LN ≤ 2 cm
	3	Discrete adenopathy in > 2 LN stations, largest LN >2 cm but ≤ 4 cm
	4	Discrete adenopathy in > 2 LN stations, largest LN >4 cm
Ecchymoses	0	Absent
	1	Discrete ecchymosis in ≤ 2 locations identified by observer
	2	Discrete ecchymosis in > 2 but < 10 locations, largest ecchymosis ≤ 5 cm
	3	Discrete ecchymosis in > 2 but < 10 locations, largest ecchymosis > 5 cm
	4	Discrete ecchymosis in > 10 locations
Edema	0	No edema
	1	Slight pitting, normal contour
	2	Moderate deeper pitting, contour preserved
	3	Deeper pitting, contour preserved
	4	Deep persistent pitting, contour not preserved, and appears puffy
Ascites	0	Positive
	1	Negative
Liver/spleen size palpable	0	Positive
	1	Negative

Disease-related symptoms at each visit will be evaluated including any changes from baseline.

2.3.4.8.5. Pharmacokinetics (PK)

Data on serum NEOD001 concentrations from this study will be pooled with data from similar samples from other studies in a population PK analysis. Population PK analyses will be reported separately from the NEOD001-201 CSR.

2.3.5. Safety Endpoints

Safety and tolerability of NEOD001 as assessed by vital signs, 12-lead ECGs, routine laboratory assessments, AEs, and immunogenicity by measurement of anti-NEOD001 antibodies.

3. SAMPLE SIZE JUSTIFICATION

For the primary endpoint, the assumed true rates for NEOD001 vs placebo are 50% and 22.5%, respectively. Based on a two-sample comparison of proportions at the $\alpha=0.05$ level of significance, a total sample size of 100 subjects (50 in the NEOD001 arm, 50 in the placebo arm) will provide $>80\%$ power based on a two-sided Cochran-Mantel-Haenszel (CMH) test. Based on the actual enrolled sample size ($N\sim 130$), the final power is 91%.

4. GENERAL STATISTICAL METHODS

4.1. Reporting Conventions

Individual subject data obtained from electronic case report forms (eCRFs), central laboratories, external sources, and any derived data will be presented in data listings by subject. The primary data source will be used for all analyses. All data listings that contain an evaluation date will contain a relative study day. Pre-treatment and on-treatment study days are numbered relative to the day of the first dose of study drug which is designated as Day 1. The preceding day is Day -1, the day before that is Day -2, etc.

All output will be incorporated into Microsoft Word rich text format (.rtf) files, sorted and labeled according to the ICH recommendations, and formatted to the appropriate page size(s).

For categorical variables, summary tabulations of the number and percentage of subjects within each category (with a category for missing data) of the parameter will be presented. Percentage calculations will be based on non-missing data, unless otherwise specified. Percentages are rounded to 1 decimal place, unless otherwise specified.

For frequency counts of categorical variables, categories whose counts are zero will be displayed for the sake of completeness. For example, if none of the subjects discontinued due to “lost to follow-up,” this reason will be included in the table with a count of 0. Percentages based on frequency counts will be presented to one decimal place, and values less than 1% will be presented as “<1%.” Values less than 100% but greater than 99% will be presented as “>99%.”

For continuous variables, the number of subjects, mean, standard deviation (SD), median, 25th (Q1) and 75th (Q3) quartiles, minimum, and maximum values will be presented. The precision of summary statistics, unless otherwise specified will be as follows: mean and median to 1 more decimal place than the raw data, and SD to 2 decimal places more than the raw data. In general, the number of decimal places should not exceed 3 decimal places unless appropriate. Confidence intervals (CIs) will be provided and will be rounded to 1 decimal place, unless otherwise specified, in the table and listing shell.

For tables where rounding is required, rounding will be done to the nearest round-off unit. For example, when rounding to the nearest integer, values $\geq XX.5$ will be rounded up to $XX+1$ (e.g., 97.5 will round up to 98), while values $<XX.5$ will be rounded down to XX (e.g., 97.4 will round down to 97).

Time-to-event data will be summarized using Kaplan-Meier (KM) methodology using 25th, 50th (median), and 75th percentiles with associated 2-sided 95% CIs (where estimable), as well as percentage of censored observations.

All statistical tests comparing groups will be conducted at the 2-sided, 0.05 level of significance, unless otherwise specified. Summary statistics for each treatment group will be presented, as well as two-sided 95% CIs comparing groups will be provided.

4.2. Computing Environment

All descriptive statistical analyses will be performed using SAS software Version 9.4 or higher, unless otherwise noted. Medical history and AEs will be coded using Medical Dictionary for

Regulatory Activities (MedDRA) version 19.0. Concomitant medications will be coded using World Health Organization (WHO) Drug Dictionary, B2 Enhanced December 2015.

4.3. Partial Dates and Unknown Times

If only a partial date is available and is required for calculation, the following standards will be applied:

- Birth Date
 - For missing day only – Day will be imputed as the middle of the month (i.e., 15).
 - For missing day and month – Day and month will be imputed as the middle of the year (i.e., 15 June).
- Death Date
 - The last date that each subject was known to be alive will be identified as the greatest date associated with the subject's completed assessments, including telephone contacts at which the subject was confirmed to be alive.
 - For missing day only – Day will be imputed as the first day of the month (i.e., 1) with the following exception: if the partial date falls in the same month as the last known alive date, then the partial date will be imputed to equal the last known alive date.
 - For missing day and month – Day and month will be imputed as the first day of the year (i.e., 1 January) with the following exception: if the partial date falls in the same year as the last known alive date, then the partial date will be imputed to equal the last known alive date.
- Diagnosis Date
 - For missing day only – Day will be imputed as the first day of the month (i.e., 1).
 - For missing day and month – Day and month will be imputed as the first day of the year (i.e., 1 January).
- Start Dates (e.g., event date, adverse event [AE] onset date, or start date of medication)
 - For missing start day only – Day will be imputed as the first day of the month (i.e., 1) with the following exception: if the partial date falls in the same month and year as the date being used in the calculation (e.g., first infusion date, informed consent date), then the partial date will be imputed to equal the date being used for the calculation.
 - For missing start day and month – Day and month will be imputed as the first day of the year (i.e., 1 January) with the following exception: if the partial date falls in the same year as the date being used in the calculation (e.g., first infusion date, informed consent date), then the partial date will be imputed to equal the date being used for the calculation.
 - Imputed start dates must be prior to the stop date.
- Stop Dates (e.g., AE resolution date or stop date of medication)

- For missing stop day only – Day will be imputed as the last day of the month (i.e., 28, 29, 30, or 31).
- For missing stop day and month – Day and month will be imputed as the last day of the year (i.e., 31 December).
- Imputed stop dates must be on or after the start date.

If a time required for calculation related to exposure is missing, the following standards will be applied:

- If start time is missing for an infusion where the volume recorded on the eCRF is greater than 0 mL then start time will be imputed as the pre-dose time of vital signs at the same visit + 1 minute. This should only be done for the first dose time within a given visit should there be more than one record.
- If stop time is missing for an infusion where the volume is greater than 0 mL then stop time will be imputed as the ‘immediately after infusion’ time of the vital signs at the same visit - 1 minute. This will only be done for the last dose time within a given visit should there be more than one record.
- If vital sign assessment times are not available, infusion start date/time is missing, and infusion stop date/time is non-missing then the start date/time will be imputed as stop date/time - 2 hours at the Month 1 Day 1 visit or as the stop date/time - 1 hour for all other visits

If vital sign assessment times are not available, infusion stop date/time is missing, and infusion start date/time is non-missing then the stop date/time will be imputed as start date/time + 2 hours at the Month 1 Day 1 visit or as the start date/time + 1 hour for all other visits. All data recorded on the case report form will be included in data listings that will accompany the CSR.

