9.2.1. Other Adverse Events: Infusion Reactions

The incidence of infusion associated TEAEs by MedDRA SOC and PT will be summarized by treatment group and presented in a listing. This is a subset of the AEs where the question “Was the event an infusion-associated adverse event?” is checked “Yes”. Summaries will be repeated for all general baseline subgroups indicated in Section 6.

A separate summary will also be presented by planned infusion number. A TEAE will be counted based on AE and infusion start dates. For example, if an AE starts after infusion #2 but before infusion #3, the AE will be counted under infusion #2.

If applicable, the incidence of anaphylactic reaction, defined as the broad algorithmic SMQ of “Anaphylactic reaction” given in [Appendix 13](#) will be summarized by treatment group.

In order to explore the temporal relationship of TEAEs that may be associated with the infusion, the incidence of all TEAEs occurring within 24 hours (1 day) of an infusion will be summarized by treatment group and presented in a listing. In addition, for this subset of TEAEs, the following will be summarized by treatment group for any infusion and at each infusion overall and by PT:

- the number and percent of subjects infused
- the number and percent subjects experiencing an event within 24 hours
- the number of the events
- descriptive statistics for the number of events per subject
- descriptive statistics for the duration (days) of the events

TEAEs will be counted as occurring within 24 hours (1 day) of an infusion if:

- the start date/time of the TEAE is not missing and the infusion start date/time \leq the start date/time of the TEAE \leq the infusion start date/time + 24 hours or
- the start time of the TEAE is missing and the TEAE start date = the infusion start date or the TEAE start date = the infusion start date + 1 day.

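### SAP 9.2.1 uses imputed adverse event onset dates to judge timing relative to infusion, so events with an unknown onset day can be misplaced in the within-24-hours and by-infusion summaries (minor)

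*SAP*

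**What the plan says.** SAP 4.3 (Partial Dates and Unknown Times) covers start dates, including adverse event onset. The default is: "For missing start day only – Day will be imputed as the first day of the month (i.e., 1) with the following exception". The exception applies when the partial date has the same month and year "as the date being used in the calculation (e.g., first infusion date, informed consent date"), and in that case "then the partial date will be imputed to equal the date being used for the calculation". A parallel rule covers a missing day and month, with matching on year alone. One limit follows: "Imputed start dates must be prior to the stop date". No substitute value is given for when that limit bites.

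SAP 9.2.1 (Infusion Reactions) contains three distinct pieces:

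- **Infusion-associated TEAEs.** These are selected by the eCRF question "Was the event an infusion-associated adverse event". Dates play no part in the selection.
- **The same subject matter by planned infusion number.** Here dates do decide the placement: "A TEAE will be counted based on AE and infusion start dates".
- **All TEAEs within 24 hours of an infusion.** The stated purpose begins "In order to explore the temporal relationship of TEAEs that may be associated with the infusion". An event without an onset time qualifies if "the start time of the TEAE is missing and the TEAE start date = the infusion start date", or if it is dated one day later.

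Neither section says how an imputed onset date is to be treated in the second and third pieces.

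**The concern.** Moving an undated onset to the first infusion date is a sensible way to settle whether an event is treatment-emergent. It does not suit a table whose purpose is timing relative to infusion, because the imputation supplies the very quantity being tabulated. An event with no onset day will normally have no usable onset time either, so it falls under the date-only branch of the 24-hour rule.

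Two kinds of error follow. Background events early in treatment can be placed on the first infusion. True reactions at later infusions can be moved away from the infusion that preceded them. The duration statistics planned for the 24-hour subset would use the same imputed start dates.

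There is also an ambiguity. SAP 4.3 names the first infusion and informed consent only as examples of the reference date, while SAP 9.2.1 compares events with every infusion. Two programmers could apply the exception differently and obtain very different counts.

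**Working it through.** The documents give no figure for this point, so there is none to reproduce.

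**Inputs from the documents.** Up to 12 infusions (SAP 2.2.1), one every 28 days (SAP 4.6), with the efficacy end-of-study target on Day 338 (SAP 4.6, Table 3). Up to 130 subjects randomized 1:1, so about 65 per arm (SAP 2.2.5).

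**Assumptions.** Background onset uniform over Days 1 to 338; exact 28-day spacing; every possible calendar start date over one year; day missing but month known; stop-date limit ignored.

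**A dated example.** First infusion 10 March, second 7 April.
- An event starting on 25 March but recorded only as March is imputed to 10 March and counted as within 24 hours of infusion 1.
- A reaction on 7 April recorded only as April is imputed to 1 April. It leaves the 24-hour count and is assigned to infusion 1.

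**Chance rate.** 12 infusions × 2 qualifying dates = 24 days; 24/338 = 7.1%.

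**First-infusion reading.**
- Onsets in the calendar month of the first infusion: 4.67% of all onset days. All are counted, whereas 13% of those days truly lie on an infusion date or the day after.
- Onsets in other months whose imputed 1st of the month happens to be an infusion date or the day after: 6.76%.
- Total counted: 4.67% + 6.76% = 11.4%, against 7.1% by chance.

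**Any-infusion reading.** 95.8% of on-treatment days lie in a calendar month containing an infusion, so about 96% of day-missing events are counted. Simulating the ±5-day visit window gives about 94% (and still about 11% on the first-infusion reading). About 8% of days lie in a month with two infusions, and SAP 4.3 has no rule for choosing between them.

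**Reactions at infusions 2 to 12, first-infusion reading.** Take a true onset on the infusion day or the day after, outside the first calendar month, with the day missing. About 11% stay in the 24-hour count, and about 95% are assigned to an earlier infusion.

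**Effect on a between-arm difference in subject incidence.** Let M be TEAEs per subject, p the share with a missing onset day, q the probability of being counted after imputation and q0 the true probability. If p is equal in both arms, the difference shrinks by the fraction 1 − exp(−M·p·(q − q0)). M and p are assumed; q and q0 come from the run with visit windows (q = 0.115 or 0.944, q0 = 0.072).

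| p | First-infusion reading, M = 5 to 10 | Any-infusion reading, M = 5 to 10 |
|---|---|---|
| 1% | 0.2–0.4% | 4–8% |
| 5% | 1–2% | 20–35% |
| 10% | 2–4% | 35–58% |

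For example, on the any-infusion reading with M = 5 and p = 5%: 5 × 0.05 × (0.944 − 0.072) = 0.218, and 1 − exp(−0.218) = 0.196. A true difference of 10.5 percentage points becomes about 8.5.

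In event counts on the first-infusion reading, 65 × 5 × p × 0.047 gives about 0.15 events per arm placed on infusion 1 at p = 1%, and about 0.8 at p = 5%.

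**The case against.** The case for leaving the text alone is substantial.

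- **The any-infusion reading is strained.** Both named examples are single dates per subject. With day and month missing, an event could match many infusions and the SAP could not choose among them. This stands: the 96% figure shows what the loose wording permits, and is not the most natural reading.
- **Partial dates may be rare.** Protocol 7.1 requires an onset date for every event, and Protocol 5.3 provides for about 90 minutes of monitoring after infusion, so reactions in the clinic are unlikely to lack a day. This also stands, and it limits the practical size.
- **Counting uncertain events is the cautious convention.** SAP 9.2 does this for treatment emergence. That is right for deciding whether an event counts at all. It is less apt for timing, where the default to the 1st of the month also removes true later reactions from their infusion. A separate row keeps the caution without asserting a date.
- **Recorded data will be listed.** SAP 4.3 puts all recorded case report form data in listings, so a careful reader could find the partial dates. That does not correct the tables.

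A reader might infer that undated events fill the infusion-reaction summary and hide a real difference between arms. The documents do not support that. The infusion-associated summary is selected by the eCRF checkbox, so an imputed date cannot bring an event into it. The default imputation is the 1st of the month, not the infusion day. SAP 9 plans no inferential safety comparison unless otherwise specified, and no document gives the share of partial dates from which a hidden difference could be argued.

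**Conclusion.** The gap is real and minor. Even on the narrow reading, the two sections together give a wrong timing for a day-missing event: all such events in the first infusion's calendar month count as within 24 hours of infusion 1 (unless the stop-date limit blocks them), against about 13% truly so, and most day-missing reactions at later infusions move to an earlier one. Overall on that reading the counted share is about 11% instead of 7%, and the shrinkage of an arm difference is at most about 2% if up to 5% of events lack a day. It becomes material only if the exception is programmed against any infusion date and partial dates are common.

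These sizes rest on uniform background timing, equal shares of partial dates in both arms, and assumed values of M and p. The tables affected are descriptive: the within-24-hours TEAE summary with its listing, and the by-infusion-number assignment. Some care is still worthwhile because true reactions may be few. Protocol 1.3.2 reports infusion-related reactions with under 1% of infusions in the completed Phase 1/2 study; at 65 × 12 = 780 infusions in the NEOD001 arm, that rate would mean fewer than 8, so a few misplaced events could be noticed.

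**What to change.** In SAP 9.2.1, state that a TEAE with an imputed onset date does not qualify for the within-24-hours count or for assignment to an infusion number, and that such events appear in a separate row and listing by arm. A sensitivity count that includes them is optional.

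In SAP 4.3, state that for adverse event onset the reference-date exception uses the first infusion date and serves treatment-emergence status only.

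The cost is two sentences, one filter on the imputation flag and one extra row. The downside is that a few possible true reactions move to the separate row. They remain in all the main TEAE tables, and the checkbox-based infusion-associated summary does not change.
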